## 5.2 Exclusion Criteria

To participate in this study the subject must **not meet any** of the following exclusion criteria:

1. Subject declined to sign the Informed Consent Form for the study.
2. Subject, if female is pregnant or is breastfeeding, or if male, with a partner who is currently pregnant.
3. Subject has positive test result for hepatitis B surface antigen or confirmed positive anti-HIV antibody test
4. Subject received study contraindicated medications including but not limited to those listed in [Table 5](#), or medications contraindicated for ritonavir or ribavirin per FDA label prior to the study drug administration and unwilling to discontinue prior to starting the study drug. For those that receive ribavirin, contraindicated medications must be discontinued at least 2 weeks or 10 half-lives prior to study drug administration, whichever is longer.
5. Use of known strong inducers of cytochrome P450 3A (CYP3A) or strong inducers of cytochrome P450 2C8 (CYP2C8) or strong inhibitors of CYP2C8 within 2 weeks of the respective medication/supplement prior to initial dose of study drug (see [Table 5](#)).
6. Clinically significant abnormalities or co-morbidities, other than HCV infection that in opinion of the investigator makes subject unsuitable for this study or drug regimen
7. Current enrollment in another interventional clinical study or prior or current use of any investigational or commercially available anti-HCV agents other than interferon or ribavirin including previous exposure to ABT450 (paritaprevir), ABT-267 (ombitasvir) or ABT-333 (dasabuvir) or receipt of any investigational product within 6 weeks prior to study drug administration
8. Prior treatment of chronic HCV infection with a direct acting antiviral agent(s): telaprevir, boceprevir, sofosbuvir, simeprevir, or other direct acting antiviral
9. History of solid organ transplant
10. Screening laboratory analyses shows any of the following abnormal laboratory results:
  - Glomerular filtration rate < 30 mL/min as estimated by the Cockcroft-Gault equation
  - Hemoglobin < 12 gram per deciliter for male
  - Hemoglobin < 11 gram per deciliter for female
11. Evidence of cirrhosis, documented by one of the following:
  - Liver biopsy histologic diagnosis: Metavir Score > 3 (includes 3 - 4 or 3/4) or Ishak score > 4
  - In the absence of liver biopsy: a FibroScan score  $\geq$  12.5 kPa
  - In the absence of a FibroScan: an APRI score > 1.5
  - In the judgment of the investigator clinical findings are consistent with cirrhosis. In general, a non-cirrhotic result from a Fibroscan will supersede evidence of cirrhosis based on APRI and a liver biopsy not showing cirrhosis will superseded both Fibroscan and APRI.
12. History of liver decompensation: ascites noted on a physical exam, imaging or other test; variceal bleeding; hepatic encephalopathy

13. Confirmed presence of hepatocellular carcinoma indicated on computed tomography, magnetic resonance, or other imaging techniques within 3 months prior to screening
14. HCV genotype performed during screening indicates infection with any genotype other than genotype 1
15. Recent history of active drug or alcohol abuse that could, in the opinion of the investigator, affect adherence to the study protocol

## **6 STUDY ASSESSMENTS**

The study procedures to be performed are outlined in Appendix A: Study Visit/ Procedures Table and discussed in detail in this section. All study data will be recorded in the subject's source documentation and appropriate case report form(s).

### **6.1 Study Procedures**

#### **6.1.1 Informed Consent**

The study and the associated risks and benefits of participating in the study will be outlined in detail by the investigator. Signed study-specific informed consent will be obtained from the subject before any study procedures are performed. Details regarding the informed consent process and documentation are provided in [Section 13.1](#).

#### **6.1.2 Eligibility Review**

An eligibility review will be documented at Screening and confirmed at Baseline/Day 1.

#### **6.1.3 Medical History**

A review of medical history will be done at screening and baseline (before treatment).

#### **6.1.4 Complete Physical Examination**

A complete physical examination will be conducted at the Screening Visit. The physical examination performed at the screening visit will serve as the baseline physical examination for clinical assessment.

Additional physical exam(s) may be performed at the discretion of investigator per standard of care. If available, data related to changes from baseline, adverse events, and participant follow-up resulting from the symptom-directed physical exam will be documented as appropriate.

#### **6.1.5 Liver Fibrosis Assessment**

Liver fibrosis assessment is comprised of aspartate aminotransferase to platelet ratio index (APRI), liver FibroScan, liver biopsy, and/or clinical finding consistent with cirrhosis.

### **6.1.6 Vital Signs, Weight, and Height**

Body temperature, blood pressure, pulse, body weight, and height will be measured at the screening visit. Optional, obtain vital signs (temperature, blood pressure, pulse), weight and height at the Baseline Visit may be done at the discretion of the investigator for Ribavirin dosing calculations.

### **6.1.7 Pregnancy Test**

Pregnancy tests are not required for female subjects with documented prior bilateral tubal ligation, bilateral oophorectomy, or hysterectomy, or for subjects who are confirmed to be postmenopausal. Confirmation of post-menopausal status measured by follicle-stimulating hormone (FSH) will be obtained at the screening visit only for all female subjects.

For females of childbearing potential:

- A serum pregnancy test will be performed at the screening visit only and sent to the local laboratory for analysis.
- Pregnancy testing will be performed on site during the study visits as specified in Appendix A: Study Visit/ Procedures Table regardless of treatment regimen. If a urine pregnancy result is positive, a confirmatory serum human chorionic gonadotropin ( $\beta$ -hCG) test will be collected and sent to the local lab for processing.
- Subjects that receive a ribavirin-containing regimen will have pregnancy tests performed in accordance with the protocol while participating in the study. Otherwise, subjects are recommended to have monthly pregnancy test throughout the treatment period and for a minimum of 7 months after the discontinuation of ribavirin, or according to the FDA approved ribavirin label and/or standard of care.

For females of childbearing potential, and males with a female partner of child-bearing potential:

- Upon completion of the study, subjects will be counseled regarding pregnancy at their last study visit with instructions to contact their healthcare provider right away in the event that they or their female partner becomes pregnant.

For subjects with positive pregnancy test during the course of the study, refer to [Section 6.3.4](#).

### **6.1.8 Clinical Laboratory Samples**

The following laboratory samples will be obtained as outlined in [Appendix A](#). Laboratory samples will be managed, processed, and resulted in accordance with KPSC standards.

#### **6.1.8.1 Hepatitis and HIV Screen**

Hepatitis B surface antigen (HBsAg), anti-hepatitis C antibody (anti-HCV Ab), and anti-human immunodeficiency virus antibody (anti-HIV Ab) will be performed at screening. A positive anti-HIV Ab test result must be confirmed. The site will report these results per local regulations, if necessary.

**6.1.8.2 Hepatitis C Virus Genotype and Subtype**

Plasma samples for HCV genotype and subtype will be collected at screening. Historical HCV genotype and subtype within 6 months of the Screening Visit is permitted and may be substituted for the screening plasma sample collection at the discretion of the investigator. Genotype and subtype will be assessed using the standard assay per Kaiser Permanente regional laboratory.

**6.1.8.3 Hepatitis C Virus RNA**

Plasma samples for HCV RNA levels will be collected as indicated in Appendix A: Study Visit/ Procedures Table. Plasma HCV RNA levels will be determined using the standard assay per Kaiser Permanente laboratory.

**6.1.8.4 Safety Monitoring Labs**

CBC with differential, creatinine, and liver panel lab tests (total bilirubin, alanine aminotransferase (ALT), and alkaline phosphatase levels (AlkPhos)) will be performed as indicated in Appendix A: Study Visit/ Procedures Table.

**6.1.8.5 Additional Labs**

At the discretion of the treating investigator, additional laboratory tests may be ordered with the study labs. If available, results from the following labs will also be collected in the study: coagulation panel (PT, PTT), INR, reticulocyte count, direct bilirubin, and electrolytes.

Consistent with standard practice, clinically significant laboratory tests must be repeated and monitored to a satisfactory clinical resolution.

**6.1.9 Concomitant Medication Assessment**

Subject's use of concomitant medications, prescription and over-the-counter including vitamins and herbal supplements, administered from the time of signing the consent through 30 days after last dose of study drug administration will be collected. The investigator or authorized designee should review concomitant medication label(s) and assess for potential drug interactions.

**6.1.10 Adverse Event (AE) Assessment**

Clinical outcome events that occur during the treatment period through post-treatment week 12 will be recorded and documented in the case report form as an AE or Serious Adverse Event (SAE). Refer to Section 9 Assessment of Safety for more information.

**6.1.11 Study Drug Dispensing**

Study drugs will be dispensed at the visits as indicated [Appendix A](#). At each visit, any remaining study drug from the previous visit will be re-dispensed to the subject.

Subjects receiving ribavirin will be provided with the Ribavirin Medication Guide at their Baseline Visit.

### **6.1.12 Study Drug Accountability/ Compliance Review**

At each visit noted in [Appendix A](#), study drug dispensation and administration reconciliation will be recorded according to the number(s) of: VIEKIRA PAK™ and ribavirin tablets (if applicable) available at each study visit. Study drug dosing will be reviewed at each study visit. Subject adherence to study protocol and study drug treatment will be monitored each visit.

## **6.2 STUDY VISITS**

### **6.2.1 Screening Visit Procedures (- 28 days to Baseline/Day 1) (Visit 1)**

The following assessments/procedures will be performed in-clinic:

- Obtain signed informed consent
- Eligibility review
- Complete medical history
- Complete physical examination
- Liver fibrosis assessment
- Obtain vital signs (temperature, blood pressure, pulse), weight and height
- Obtain Pregnancy Test, serum  $\beta$ -hCG
- Obtain HCV Genotype and Subtype
- Obtain the following labs. Note: Laboratory results obtained within three (3) months of Screening Visit may be used at the discretion of the investigator.
  - HBsAg and anti-HCV Ab
  - Anti-HIV Ab
  - HCV RNA
  - CBC with differential
  - Creatinine
  - Liver panel (ALT, Alkaline Phosphatase, Total Bilirubin), AST and Direct Bilirubin
  - Additional labs as determined by the investigator
- Review concomitant medications

### **6.2.2 Baseline/Day 1 Procedures (Visit 2)**

The following assessments/procedures will be performed in-clinic:

- Confirm inclusion and exclusion criteria to determine eligibility
- Review Medical History

---

 Pregnancy test not required for female subject with documented bilateral tubal ligation, bilateral oophorectomy, or hysterectomy, or for postmenopausal subjects as confirmed by FSH test

 Medical record documentation of HCV genotype and subtype within the last 6 months may be substituted for the screening plasma sample collection

- Optional, obtain vital signs (temperature, blood pressure, pulse), weight and height at the discretion of the investigator
- Pregnancy Test, Serum or Urine
- Additional labs as determined by the investigator
- Review concomitant medications
- Review for AEs
- Study Enrollment/Treatment assignment
- Dispense study drug by providing the subject with a new two week supply of Viekira Pak, and if applicable, provide subject with the Ribavirin Medication Guide. Subjects should be instructed to have their first dose same day that they can take a full day course of the study drug (e.g. subject seen in the afternoon should be instructed to take their first dose the next day)
- Study drug accountability

### **6.2.3 Treatment Period**

Treatment visits should be based on the subject's Baseline Visit date.

If a subject discontinues or withdraws from the study during the treatment period, he/she should be encouraged to complete the End of Treatment (EOT) Procedures ([Section 6.2.3.3](#)) and the Early Termination Visit ([Section 6.2.4.2](#)) within 14 days of the last study treatment dose. In the event that subject is unable to complete the visit(s) but willing to provide survival status, the study site staff should contact the subject within 14 days to collect the information.

#### **6.2.3.1 Week 2 (Visit 3)**

The following assessments/procedures will be performed in-clinic:

- Obtain labs:
  - HCV RNA
  - CBC with differential, only required for subjects receiving ribavirin (Genotype 1a)
  - Creatinine
  - Liver panel (ALT, Alkaline Phosphatase, Total Bilirubin), AST and Direct Bilirubin
  - Additional labs as determined by the investigator
- Review concomitant medications
- Review for AEs
- Dispense study drug by providing the subject with a new two week supply of Viekira Pak and re-dispensing the remaining RBV
- Study drug accountability

#### **6.2.3.2 Week 4 (Visit 4) and Week 8 (Visit 5)**

The following assessments/procedures will be performed in-clinic:

- Pregnancy Test, Serum or Urine
- Obtain labs:
  - CBC with differential
  - Creatinine
  - Liver panel (ALT, Alkaline Phosphatase, Total Bilirubin), AST and Direct Bilirubin
  - Additional labs as determined by the investigator
- Review concomitant medications
- Review for AEs
- Dispense study drug
- Study drug accountability

### **6.2.3.3 Week 12 (Visit 6) - End of Treatment (EOT) Procedures**

The following assessments/procedures will be performed in-clinic:

- Pregnancy Test, Serum or Urine
- Obtain labs:
  - HCV RNA
  - CBC with differential
  - Creatinine
  - Liver panel (ALT, Alkaline Phosphatase, Total Bilirubin), AST and Direct Bilirubin
  - Additional labs as determined by the investigator
- Review concomitant medications
- Review for AEs
- Study drug accountability

### **6.2.4 Post-Treatment (PT) Period**

Post-treatment visits should be based on the subject's last dose of the study drug.

If a subject discontinues or withdraws from the study during the post-treatment period, he/she should be encouraged to complete the Early Termination Visit ([Section 6.2.4.2](#)) except when the reason for discontinuation is confirmed virologic failure as described in [Section 6.3.3](#). If a subject is unable to complete the Early Termination visit but willing to provide survival status, the study site staff should contact the subject to collect the information.

#### **6.2.4.1 Post-Treatment (PT) Week 4 (Visit 7)**

The following assessments/procedures will be performed either in-clinic, or remotely by phone with labs collected at the subject's nearest laboratory facility:

- Pregnancy Test, Serum or Urine
- Obtain labs:

- HCV RNA
- CBC with differential
- Creatinine
- Liver panel (ALT, Alkaline Phosphatase, Total Bilirubin), AST and Direct Bilirubin
- Additional labs as determined by the investigator
- Review concomitant medications
- Review for AEs

#### **6.2.4.2 Post-Treatment (PT) Week 12 (Visit 8) - End of Study/ Early Termination (ET)**

The End of Study Post-Treatment Week 12 visit will be completed at the conclusion of the post-treatment period.

Early Termination Visit should be completed when a subject discontinues or withdraws from the study during either the Treatment or Post-treatment, except when the reason for discontinuation is confirmed virologic failure ([Section 6.3.3](#)).

If a subject discontinues or withdraws from the study during the treatment period, he/she should be encouraged to complete the End of Treatment (EOT) Procedures ([Section 6.2.3.3](#)) and the Early Termination Visit ([Section 6.2.4.2](#)) within 14 days of the last study treatment dose. In the event that subject is unable to complete the visit(s) but willing to provide survival status, the study site staff should contact the subject within 14 days to collect the information.

If a subject discontinues or withdraws from the study during the post-treatment period, he/she should be encouraged to complete the Early Termination Visit ([Section 6.2.4.2](#)) except when the reason for discontinuation is confirmed virologic failure as described in [Section 6.3.3](#). If a subject is unable to complete the Early Termination visit but willing to provide survival status, the study site staff should contact the subject to collect the information.

The following assessments/procedures will be performed in-clinic, or remotely by phone with labs collected at the subject's nearest laboratory facility:

- Pregnancy Test, Serum or Urine
- Obtain labs:
  - HCV RNA
  - CBC with differential
  - Creatinine
  - Liver panel (ALT, Alkaline Phosphatase, Total Bilirubin), AST and Direct Bilirubin
  - Additional labs as determined by the investigator
- Review concomitant medications
- Review for AEs

### **6.2.4.3 Unscheduled Visits and Labs**

Unscheduled visits and labs may be done as determined by the investigator to protect the safety of the subject, such as in the case of AEs.

### **6.2.4.4 Unscheduled Drug Dispensing**

Unscheduled drug dispensing to prevent treatment interruption requires prior approval from the Sponsor-Investigator or designee.

## **6.3 Subject Discontinuation**

### **6.3.1 Subject Initiated Discontinuation**

Each subject has the right to withdraw from the study at any time for any reason. Subjects who discontinue from the study regardless of cause should be encouraged to complete the Early Termination Visit within 14 days of the last treatment dose. Ideally for study drug discontinuation, this should occur on the day of study drug discontinuation, and prior to the initiation of any other anti-hepatitis C virus therapy. However, these procedures should not interfere with the initiation of any new treatments or therapeutic modalities that the investigator feels are necessary to treat the subject's condition.

In the event that subject is unable to complete the visit but willing to provide survival status, the study site staff should contact the patient within 14 days of the last study dose to collect the information.

Following discontinuation of study drug, the subject will be treated in accordance with the investigator's best clinical judgment. The last dose of any study drug and reason for discontinuation from the treatment period will be recorded in the case report form.

Withdrawal of consent for the study will be documented in the subject's study records and reported to the PI and/or designee.

### **6.3.2 Investigator Initiated Discontinuation**

The investigator may also discontinue a subject from the study at any time for the following reasons:

- Subject or subject's partner experiences AE or toxicity from the study drug that warrants discontinuation, or
- Subject is noncompliant (e.g. missed treatment doses, or missed visits) with the protocol, or
- If a subject has an ongoing AE or an unresolved laboratory result that is significantly outside of the reference range at the time of study drug discontinuation, the investigator will attempt to provide follow-up until a satisfactory clinical resolution of the laboratory result or AE is resolved.

### **6.3.3 Discontinuation of Subjects Meeting Virologic Failure Criteria**

The following criteria will be considered evidence of virologic failure:

- Confirmed increase from nadir in HCV RNA, defined as two consecutive HCV RNA measurements  $> 1 \log_{10}$  IU/mL above nadir, at any time point during treatment
- Confirmed HCV RNA  $\geq$  lower limit of quantification, defined as two consecutive HCV RNA measurements  $\geq$  lower limit of quantification, at any point **after** HCV RNA less than lower limit of quantification

Confirmatory testing for the above criteria should be completed. Subjects receiving study drug treatment should remain on treatment until the virologic failure has been confirmed.

- If any of the above criteria are confirmed for subjects during study drug treatment, the subject will discontinue treatment.
- If any of the above criteria are confirmed for subjects during the post-treatment phase of the study, the subject will be discontinued from the study.

### **6.3.4 Pregnancy**

In the event that a positive result is obtained on a pregnancy test for a subject or a subject reports becoming pregnant during the treatment period, the administration of ribavirin (if applicable) to that subject must be discontinued immediately. The investigator is also encouraged to report the pregnancy information to the voluntary ribavirin pregnancy registry, if applicable.

Direct-acting antiviral agents may be continued at the Sponsor-investigator's discretion after discussion with the subject, if the benefit of continuing direct acting antiviral agents is felt to outweigh the potential risk. Subjects will be monitored for sustained virological response in the post-treatment period per protocol.

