### 3.4 Study Duration

#### Study Discontinuation

Southern California Permanente Medical Group (SCPMG) reserves the right to terminate this study at any time due to the incidence or severity of adverse events in this study that indicate a potential health hazard to subject or partner.

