#### 4.5 Dose Modification

VIEKIRA PAK will not be dose-modified.

Ribavirin will be adjusted for renal impairment subjects. Ribavirin will be dose-modified for decreases in hemoglobin or decreased glomerular filtration rate as per the package insert or per the clinical judgment of the investigator.

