**4.6.2 Ribavirin**

The primary toxicity of ribavirin is hemolytic anemia. The anemia associated with ribavirin therapy may result in worsening of cardiac disease that has led to fatal and nonfatal myocardial infarctions. Patients with a history of significant or unstable cardiac disease should not be treated with ribavirin.

Significant teratogenic and embryocidal effects have been demonstrated in all animal species exposed to ribavirin. In addition, ribavirin has a multiple-dose half-life of 12 days, and so it may persist in nonplasma compartments for as long as 6 months. Therefore, ribavirin therapy is contraindicated in women, who are pregnant and in the male partners of women who are pregnant. Extreme care must be taken to avoid pregnancy during therapy and for 6 months after completion of treatment in both female patients and in female partners of male patients who are taking ribavirin therapy. At least two reliable forms of effective contraception must be utilized during treatment and during the 6-month post-treatment follow-up period. Refer to the Ribavirin Package Insert for more information.

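### The mandatory ribavirin stop for pregnancy covers a pregnant subject but not a male subject whose partner conceives, although the protocol contraindicates ribavirin in both

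*Combined protocol and SAP*

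**What the plan says.** Section 4.6.2 names two groups: "ribavirin therapy is contraindicated in women, who are pregnant and in the male partners of women who are pregnant". Exclusion 2 in Section 5.2 applies the same pair at entry. It bars pregnant women and also the subject "if male, with a partner who is currently pregnant". Section 6.2.2 has the site repeat the check on Day 1 before drug is handed out: "Confirm inclusion and exclusion criteria to determine eligibility".

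After Baseline, the one mandatory pregnancy rule for ribavirin is in Section 6.3.4. It applies when "a positive result is obtained on a pregnancy test for a subject or a subject reports becoming pregnant during the treatment period", and it stops ribavirin in that subject. The direct-acting antivirals may continue at the Sponsor-Investigator's discretion.

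The partner, or a change to ribavirin, also appears in these places:
- Section 4.5: "Ribavirin will be dose-modified for decreases in hemoglobin or decreased glomerular filtration rate". Pregnancy is not a named trigger.
- Section 6.3.2: the investigator may withdraw a subject when the subject or the subject's "partner experiences AE or toxicity from the study drug that warrants discontinuation".
- Section 3.4: the study as a whole may be ended for a "potential health hazard to subject or partner".
- Section 6.1.7: at the last study visit, subjects are told to contact their healthcare provider if they or a female partner become pregnant.

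At Week 2 the site is to "Dispense study drug by providing the subject with a new two week supply of Viekira Pak and re-dispensing the remaining RBV". Study drug is dispensed again at Weeks 4 and 8.

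**The concern.** At entry the protocol treats the two contraindicated groups alike. During treatment it does not. A man whose partner is pregnant on Day 1 is excluded. A man whose partner conceives two weeks later falls under no rule in the protocol body that requires his ribavirin to stop, although the stated contraindication is the same.

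Detection is also one-sided. Women of childbearing potential have pregnancy tests at Weeks 4, 8 and 12. The visit lists for Weeks 2, 4 and 8 contain no corresponding question to men.

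What is at stake is continued fetal exposure to a drug for which 4.6.2 reports teratogenic and embryocidal effects in every animal species exposed. It is not the primary estimate.

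**Working it through.** **Coverage of the rules.** The protocol gives no figure to reproduce here, so the check sets the sections side by side.

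| Rule | Pregnant subject on ribavirin | Man on ribavirin, partner pregnant |
|---|---|---|
| 4.6.2 contraindication | yes | yes |
| Exclusion 2, confirmed at Baseline | yes | yes |
| 6.3.4 mandatory stop | yes | no |
| 4.5 ribavirin modification | not named | not named |
| 6.3.2 withdrawal | optional; needs an adverse event or toxicity | optional; needs an adverse event or toxicity |
| Scheduled check during dosing | tests at Weeks 4, 8 and 12 | none listed |
| 6.1.7 instruction | last visit | last visit |

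Two further provisions bear on the topic. Section 6.1.12 has adherence to the protocol monitored at each visit, and two-method contraception is a protocol requirement for these men (5.1, item 6). Section 9.1.2 counts a congenital anomaly as a serious adverse event. Neither requires a stop, and an anomaly is known too late to guide dosing.

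**Dosing that a stop could avert.** Treatment lasts 12 weeks (Table 4), and visits have a window of ±5 days, which is ±0.7 weeks (Appendix A). Remaining dosing = 12 − visit week:
- Week 2: 12 − 2 = 10 weeks (9.3 to 10.7)
- Week 4: 12 − 4 = 8 weeks (7.3 to 8.7)
- Week 8: 12 − 8 = 4 weeks (3.3 to 4.7)
- Week 12: essentially 0

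A conception after Day 1 would rarely be recognised by Week 2, if recognition takes about two weeks or more (an assumption). For the case at issue, the realistic range is therefore about 8 weeks or less.

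**Timing of the 6.1.7 instruction.** The last visit is at post-treatment Week 12, so 84 ± 5 = 79 to 89 days after the last dose in a completer. All dosing has ended by then.

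**Number of men concerned.** The genotype 1a group is expected to be about 100 (80 to 120; Section 8.3.1). The documents do not give the sex split. If 50% to 65% are men (an assumption), 80 × 0.50 = 40 to 120 × 0.65 = 78 men would receive ribavirin. Fewer than that would have a partner of childbearing potential.

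**Efficacy cost of stopping.** The only figure in the documents is for no ribavirin at all in treatment-naïve genotype 1a (Section 1.2):
- With ribavirin: 97/100 = 97.0%.
- Without ribavirin: 90.2% of 205, reconstructed as 185/205.
- Difference: 6.8 points. The Newcombe 95% interval is 0.4 to 12.0. It is preferable to a Wald interval (1.5 to 12.0) with rates this close to 100%.
- Effect of one such man on the arm's expected SVR12: 6.8/100 ≈ 0.07 points. The range runs from 0.4/120 ≈ 0.003 to 12.0/80 = 0.15.

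Table 1 has no ribavirin-free result for treatment-experienced genotype 1a, and the documents give none for a stop partway through. The loss in those cases is unknown.

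**The case against.** The strongest reply is that the protocol does take a position. The contraindication in 4.6.2 concerns therapy, not only entry. The sentences after it require care to avoid pregnancy during therapy, including in female partners of male patients. Sections 4 and 4.6.2 send the investigator to the package insert. An investigator who knows of a partner's pregnancy therefore has clear grounds to stop, and on this view 6.3.4 lacks only a cross-reference. Instructions to men would also naturally sit in the consent form, the subject information sheet and the Ribavirin Medication Guide that 6.1.11 requires at Baseline. None of these was available.

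Much of this stands, and it limits the point. A reader might infer that the protocol permits continued dosing, or that men go uninstructed during treatment. The documents support neither: 4.6.2 speaks against continued dosing, and the subject documents have not been seen. A reader might also take 10 weeks as the avoidable exposure. A pregnancy known at Week 2 would mostly have begun before Baseline, where exclusion 2 applies. Nor does it follow that the Sponsor-Investigator would never hear of a subject's pregnancy, since continuing the antivirals already needs that person's discretion.

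The reply does not explain why the two groups differ. Section 4.6.2 contraindicates ribavirin in pregnant subjects as well, yet the authors still wrote an explicit mandatory stop for them. The grounds in 4.6.2 also help only once the pregnancy is known, and no listed on-treatment procedure asks about it.

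**Conclusion.** The concern holds as a gap in the protocol body. The mandatory stop and the visit schedule, followed as written, leave out one of the two groups in whom the protocol itself contraindicates ribavirin. It should be fixed because the remedy is nearly free, not because harm is likely. With two-method contraception required, few events are expected, possibly none.

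A stop would avert about 8 weeks of dosing if the pregnancy is known at Week 4 and about 4 weeks if known at Week 8. It would not avert exposure at conception. The primary analysis is essentially unaffected.

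Confidence is high on the wording. It is lower on the practical size, which rests on an assumed recognition time, an assumed share of men, and unseen subject documents that may already close part of the gap.

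**What to change.** 1. In 6.3.4, add as a trigger that the female partner of a male subject receiving ribavirin becomes pregnant during treatment. Require immediate ribavirin discontinuation in that man, and keep the existing option to continue the direct-acting antivirals.
2. Give the 6.1.7 partner instruction at Baseline as well as at the last visit, and ask men to notify the study site.
3. At Weeks 2, 4 and 8, ask men on ribavirin about partner pregnancy within the adverse event review already scheduled.

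The cost is one clause, one sentence and one question at three existing visits, with no new procedure. If the subject documents already carry the Baseline instruction, item 2 only aligns the protocol with them. The downside is a possible loss of efficacy in a man who stops early. Section 6.3.4 already accepts that trade-off for pregnant subjects.
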